1.0 OBJECTIVES

[figure not shown]
The introduction of large-scale genomic testing in medicine promises to transform patient care. Cancer is at the leading edge of this revolution and hundreds of thousands of cancer patients receive tumor genomic testing yearly. Understanding how genomic information is conveyed in the context of cancer has broad relevance across the spectrum of human disease. Early evidence reveals that despite rapid adoption of genomic testing in cancer, many patients fail to comprehend basic information about cancer genetics or the defining genomic characteristics of their disease. For example, many breast cancer patients lack knowledge about their own tumor biomarkers and such knowledge deficiencies have been associated with lower adherence to highly effective targeted therapies.¹ Given that better-informed patients can more effectively engage in their care, and that greater knowledge about cancer and one's personal health characteristics is associated with improved cancer-related outcomes, there are significant concerns that patients' genomic knowledge deficits may contribute to poor quality care. In this context there is an urgent need to educate patients about cancer genomics generally, and their sequencing results specifically, in a format that is usable, useful, and that easily integrates into existing clinical workflows.

The goal of our research program is to improve the delivery of high-quality precision cancer medicine. In the current study, we plan to test the efficacy of providing patients with direct access to their sequencing results and information on cancer genomics through a web-based interface, Helping Oncology Patients Explore-Genomics (HOPE-Genomics).

2.0 BACKGROUND AND RATIONALE

We are in the midst of a genomic revolution; more than 250,000 human genomes have been sequenced, generating over a petabase of genomic data. If these data were used correctly, they could save hundreds of thousands of lives each year. However, there is a disconnect between genomic discovery and clinical care. Physicians frequently misinterpret genomic information and patients often don't understand their own test results. To address these care gaps, we have developed tools to help physicians and patients interpret, use, and share genomic data. Our work has been primarily in cancer and we aim to further develop and test tools that overcome gaps in genomic care delivery. Our overarching goal is to optimize the integration of whole-exome and whole-genome sequencing (WES, WGS) into general clinical practice.

The ineffective implementation of genomic discoveries produces a ubiquitous "last mile" problem.^{1,2} For example, *BRCA* testing has been guideline-endorsed for 20 years but most patients who could benefit from testing are not sequenced. Moreover, data misinterpretation and poor communication has devastating consequences, including unnecessary organ removal, missed disease prevention opportunities, and premature death. Without rigorous interventions to address these problems, the societal investment of billions of dollars in genomics may yield little real world payoff.¹

Most attempts to improve genomics-based care have targeted only one clinical factor and have focused on a few genes. Multi-level interventions, ones that target multiple factors, are hypothesized to be more effective.³ Furthermore, tools are needed to communicate WES/WGS data to physicians and patients, including non-English speakers. Our work will improve care by transforming genomic communication from a traditional model of linear information flow to one that puts patients at the center of communication and enables them to seamlessly connect with providers, labs, and family members (Figure 1).

This proposal builds on our prior research and preliminary data which demonstrates that patients frequently don't know that they have had sequencing or understand the implications of their results, and that many physicians don't understand sequencing information.⁴⁻¹⁰ In order to overcome these problems, we developed a patient intervention called HOPE-Genomics. HOPE-Genomics is an interactive, web-based, point-of-care tool that 1) educates patients about genomics, 2) enables direct-to-patient return-of-results, and 3) facilitates sharing of genomic results within families. Based on pilot testing, we have found this intervention to be highly acceptable to patients and clinicians.

2.1 Specific Aims

In the proposed work we aim to:

- **Aim 1:** Test the efficacy of the HOPE-Genomics intervention in improving patient knowledge of genomics (recall rates)
 - Hypothesis:* The use of HOPE-Genomics will result in higher rates of patient knowledge (recall rates) of genomics and their personal test results
 - Strategy:* We will conduct a randomized controlled trial of HOPE-Genomics as an educational tool among patients receiving WES/WGS as a part of their clinical care.
- **Aim 2:** Test the efficacy of the HOPE-Genomics intervention in improving patient receipt of guideline-concordant care
 - Hypothesis:* The use of HOPE-Genomics, will result in higher rates of uptake of evidence-based genetically-guided care vs. usual care.
 - Strategy:* We will conduct a randomized controlled trial of HOPE-Genomics among patients who receive WES/WGS as a part of their clinical care.

3.0 PARTICIPANT NUMBER, RECRUITMENT, COHORT CHARACTERISTICS AND ELIGIBILITY

3.1. Participant Number

We anticipate recruitment and enrollment of approximately 465 patients for this study and assume a 10% overall attrition rate after enrollment. We will recruit from among patients who consent to the COH IRB 07047 Precision Medicine protocol and who have been or had been diagnosed with cancer. For 07047 overall, we estimate approximately 4000 total patients in year 1 of Precision Medicine (beginning CY 2021), 6000 total patients in year 2, and larger numbers yet in subsequent years, demonstrating likely feasibility. Given that patients who consent to 07047 may receive WES (e.g. GEM ExTra), Panel

Testing (e.g. HopeSeq), and/or germline (e.g. Invitae) as part of their care, they will have the genomic testing that is necessary for this education intervention study.

3.2. Duration of Study

Protocol will end when enrollment has reached limit of 465, and all study activities have concluded.

3.3. Recruitment

We will enroll approximately 465 patients from City of Hope Duarte main campus and community locations. Patients will be identified in collaboration with the COH Precision Medicine (PM) team. [name], the study PI, is the Deputy Director of the Center for Precision Medicine and works closely with the entire PM team. Patients who have consented to COH IRB 07047, who are having genomic sequencing through 07047, and who have solid tumor diagnoses (see eligibility criteria below) will be eligible to participate. Patients will provide consent to this protocol at the start of their participation in the study and will subsequently be randomized into either the control arm (i.e., Usual Care), the Return of Results arm or the Return of Results plus Pretest Education arm.

In Clinic Recruitment

Potentially eligible patients will be approached by study team members during clinic visits for verbal informed consent. Patients will either be enrolled on site or given a study packet containing an invitation letter, informed consent document, return envelope, and a postcard to denote interest in participating or declination. Patients who do not return the postcard within 2-3 weeks will be contacted by a study team member to reassess interest in participating. Patients will be contacted either by telephone or web-conference or will be contacted at their next COH appointment in person. For patients interested in participating, study staff will schedule a verbal informed consent session by telephone, web-conference, or a patient's next COH appointment in person.

Remote Recruitment

When in-clinic recruitment is not feasible, potentially eligible patients will be contacted by study team members via telephone/email to gauge interest and potentially schedule a verbal consent session. If the patient cannot be reached, participants will be mailed a study information packet containing an invitation letter, informed consent document, return envelope, a postcard to denote interest in participating or declination. Study staff will also email patients to encourage contact. Patients who do not return the postcard within approximately 7-10 days weeks will be contacted by a study team member to reassess interest in participating, either by telephone or web-conference. Study staff will schedule a verbal informed consent session with patients who are interested in participating, either by phone or web-conference.

Waiver of Documentation of Informed Consent

We have requested a waiver of documentation of informed consent for patient participants in the randomized clinical trial. This portion of the study qualifies for waiver of documentation of informed consent under the criteria established by the [Office of Human Research Subjects Protection](#) that:

- (1) The research involves no more than minimal risk to the subjects;
- (2) The waiver or alteration will not adversely affect the rights and welfare of the subjects;

- (3) The research could not practicably be carried out without the waiver or alteration; and
- (4) Whenever appropriate, the subjects will be provided with additional pertinent information after participation.

This randomized clinical trial entails data collection through surveys and data from existing medical records, which fall under these criteria.

Although we will be requesting a waiver of documentation of informed consent, study staff will fully review the information sheet that contains all elements of informed consent with the participant before the participant starts any study activities. During patient recruitment, the study staff will keep additional documentation that information sheet was reviewed with the participant, through OnCore and REDCap systems.

3.4. Cohort Characteristics and Eligibility

3.4.1 Patient Participants

Patients will be eligible if: 1) they are enrolled in COH IRB 07047, 2) have a cancer diagnosis, 3) they are having somatic, germline or paired somatic/germline sequencing, 4) they are fluent in English, 5) they have an ECOG performance status of 0-2, and 6) they are ≥ 18 years old.

Patients will be ineligible if they 1) are unable to provide informed consent.

3.4.2 Cohort Characteristics

In accordance with NIH guidelines, women and members of minority groups and their subpopulations will be included in this protocol. We will aim for the proportion of minority participation in the study to be representative of the patient population seen by our clinics at the City of Hope Cancer. The following percentages of racial and ethnic groups constitute the City of Hope clinic population: 15% Hispanic, 2% African American, 5% Asian, 0.2% American Indian/Alaska Native, 0.2% Native Hawaiian or Other Pacific Islander and 78% are Caucasian.

4.0 STUDY PROCEDURES

4.1. Informed Consent and Baseline Survey

Potentially eligible patients will be approached by study team members for verbal informed consent, either by mail/ email, during clinic visits, or by phone. Patients will receive a study packet that will contain an invitation letter, interest postcard, return envelope, and informed consent document. Patients will be randomized into one of three arms immediately after enrollment. Arm 1 is usual care, Arm 2 is return of results only in the HOPE-Genomics tool, and Arm 3 is return of results plus pretest education in the HOPE-Genomics tool.

Arm 1 patients will receive

a pamphlet (20430 Educational Brochure in iRIS) about WES after they enroll. Their clinician will return their genomics test results in a typical manner, without the assistance of the HOPE-Genomics tool.

Arm 2 patients will receive their genomics test results both from their clinician and from the HOPE-Genomics tool but will only view the tool after their results are available. Arm 3 patients will view the HOPE-Genomics tool (containing educational content) before their sequencing results are available. These patients will also receive their genomics test results both from their clinician and from the HOPE-Genomics tool. After completing all study surveys at 9 months post results disclosure, participants in Arm 1 (usual care), will receive access to the HOPE-Genomics tool, which will contain both the educational information and the personalized genomics results.

Table 1: Outcome and covariate data collection

			Patient surveys			MRA
	Baseline	Pre-edu. survey	T1	T2	T3	
Genetic Care outcomes						
MD recommendations						
Screening, surgery, meds			X	X	X	X
Referrals GC, specialists			X	X	X	X
Cascade testing			X	X	X	X
Patient utilization/behavior						
Screening, surgery, meds			X	X	X	X
Consult GC, specialists			X	X	X	X
Inform family members			X	X	X	
Cascade testing			X	X	X	
Patient-centered outcomes						
Recall of results	X		X	X	X	X
Understanding of results			X	X	X	
Genomic knowledge	X	X	X	X		
Engagement in care			X	X	X	
Information seeking				X		
Psychosocial impact	X		X	X	X	
Follow up outcomes						
HOPE-Genomics usability			X	X		
Satisfaction with MD-patient communication and care			X	X		
Covariates						
Socio-demographics	X					X
Clinical information						X
Other (e.g., health literacy)	X					X

Medical record abstraction (MRA); Post disclosure: 10 days (T1); 3 months (T2); 9 months (T3); Medications (Meds); Genetic counseling (GC); Physician (MD)

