4.1.1 Patient Baseline Survey

At time of consent, patients will complete the baseline survey. Baseline survey outcomes are detailed in Table 1. We will follow standard survey methods as outlined by Dillman^{2,3} (e.g., contact type and intervals; mail/email/in-person reminders) to ensure high response rates. The survey will be administered in one of the following ways, according to patient preference: (1) mailed to the participant, along with a return envelope, (2) provided electronically and/or by text message via REDCap survey link, or (3) completed over a scheduled phone or Zoom call with a study staff member. For patients who complete the baseline survey via phone or Zoom call, study staff will not assist them in selecting the correct answers for questions pertaining to their understanding of cancer and genetics.

Germline sequencing knowledge will be measured using an adapted version of the UNC Genomics Testing Knowledge Scale¹, a validated 25-item measure developed by Langer and colleagues to evaluate overall understanding of genomics and health. We will also assess patients' knowledge of the implications of WES on 1) personal cancer risk, 2) family cancer risk, and 3) genetics generally.

General cancer genomics knowledge will be assessed using a modified form of a 12-item measure developed by Blanchette and colleagues.⁵ The measure assesses three domains of cancer genomic knowledge: 1) general understanding of cancer, 2) how biological changes influence cancer, and 3) the potential implications of genomic testing in cancer. Higher general cancer genomic knowledge has been associated with higher levels of education, higher personal income and patients' perceived ability to provide informed consent for genomic testing.

Knowledge about the use of genetic testing in cancer will be assessed using a 6-item measure developed by Roth, Gray and colleagues for the Lung-MAP study (unpublished). The measure assesses participant's knowledge of why genetic testing is used in cancer care (e.g., to help select a treatment, to predict response to treatment). Eight items have been added in the following content areas: 1) use for cancer staging, 2) use to time cancer onset, 3) use to predict treatment efficacy, 4) use for clinical trials, 5) use to monitor cancer treatment, 6) use to identify a cancer's location, 7) use to determine metastasis, and 8) use to assess cancer risk.

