4.3 Tool Access and Patient Pre-Education Survey

After enrollment, all participants will be provided with a hard-copy or electronic educational pamphlet about whole-exome sequencing (WES). Patients in the Return of Results plus Pre-test Education arm will be provided with login and dual-factor authentication instructions and have immediate access to educational content in the tool, with their sequencing results to become available in the tool shortly after their results are available in Epic. Patients in the Return of Results Only arm will not be able to see tool content until their genomic test results are available (e.g., ~2-6 weeks after sample collection). Patients in the Usual Care arm will have access to the tool content after completing all study surveys, approximately ~9 months after their sequencing results are available.

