
To improve patient compliance to study requirements, all patients will be presented with the option to opt-in to receive text message reminders related to study participation and to receive access to unique survey links. Patients will have the option to opt in and opt out of receiving text message reminders at any point during their participation; the decision would not affect their participation in the study. For patients who have agreed to provide their mobile number for text message reminders, this method will be used to supplement electronic communication reminders to encourage and facilitate intervention use. Mobile numbers will be collected solely for the purposes of communicating study-related requirements to patients and will not be used to disclose any PHI nor will they be shared for purposes beyond this study and without patient consent. Information detailed in text message correspondences will reference time points and reminders of which patients will need to:

1. Complete a study procedure (e.g., view HOPE-Genomics platform, complete a survey)
2. Be provided with unique survey links generated by REDCap (i.e., links for Baseline, Pre-test Education, 10-day Follow-up, 3 Month Follow-up and 9 Month Follow-up surveys).

Patients who have opted to receive reminders through their mobile phone will receive an initial message acknowledging their opt-in. Frequency of follow-up reminders to complete study procedures will be dictated by patient preference (i.e., patients prefer reminders only by text message), study arm assignment, and/or with regards to timeliness of completion of study requirements. Frequency of text messages will mimic the schedule for automated email reminders:

- **Baseline Survey:** every 96 hours
- **Pre-Test Tool Viewing (Arm 3):** 24 hours after login instructions sent
- **Pre-Test Survey:** every 96 hours
- **HOPE Tool Viewing (Arms 2/3):** 5 days after login instructions sent
- **All follow-up surveys:** Every 2 weeks

There will be a total of five time points of which patients will be provided survey links through text message. These time points correspond to the required completion of surveys as follows: Baseline survey, Pre-test Education survey, 10-day Follow-up survey, 3 Month Follow-up survey and 9 Month Follow-up surveys.

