Appendix G: Patient Script to Setup Access to HOPE-Genomics tool – RoR + Intervention Arm

Dear [PATIENT NAME],

This is the HOPE-Genomics Team from City of Hope. You may remember speaking with [consenter] about your participation in the HOPE-Genomics study, involving a web-based education tool for patients with genetic testing at City of Hope. Thank you for completing your first survey for the study!

At this time, we would like to invite you to log into and view the HOPE-Genomics before your results are ready. The tool contains helpful information, including a video, that explains the details of genomic testing and its implications for your health. You may log into the tool by clicking the following link: <https://hopegenomics.coh.org/login>.

Once you have viewed the tool, we will send you a follow-up survey. We have also attached instructions on how to access the tool.

If you have any problems accessing the tool, we can accommodate in-person visits at City of Hope Duarte campus or remote visits using web conferencing (i.e. Zoom). Please call [INSERT CRA's PHONE NUMBER] or email us at [contact] if you would like to schedule an appointment to speak with study staff.

If you have any additional questions about this research study, please call the Principal Investigator, [name] at [contact] or the Clinical Research Coordinator, [name] at [contact]. You can also reach the Institutional Review Board at City of Hope by calling [contact].

Thank you for all your help with our research at City of Hope, and we look forward to hearing from you!

The HOPE-Genomics Team

[name], [name], [name], [name], and [name]

Division of Clinical Cancer Genomics

Medical Oncology and Therapeutics Research

Department of Population Sciences

City of Hope Comprehensive Cancer Center

[name]

[name]

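### Section 4.3 opens the tool to Arm 3 without waiting for the baseline survey, so some Arm 3 baseline knowledge scores could be taken after exposure

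*Combined protocol and SAP*

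**What the plan says.** **Randomisation.** Section 3.3: "Patients will provide consent to this protocol at the start of their participation in the study and will subsequently be randomized". Section 4.1: "Patients will be randomized into one of three arms immediately after enrollment". Neither names a completed baseline survey as a step in between.

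**Baseline survey.** Section 4.1.1 sets the nominal time: "At time of consent, patients will complete the baseline survey". The same paragraph lets the patient choose to have it "mailed to the participant, along with a return envelope", sent as a REDCap link, or done on a scheduled call. The reminder schedule in section 4.3 reads "Baseline Survey: every 96 hours", so completion some days after consent is foreseen.

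**Arm 3 tool access.** Section 4.3 gives Arm 3 login instructions after enrolment, and says these patients "have immediate access to educational content in the tool". It sets no baseline condition. Staff contact Arm 3 within about 24 hours of sending the login to encourage viewing, and the text-message schedule has a prompt at 24 hours.

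**Scripts.** Appendix G, the Arm 3 login invitation, opens with "Thank you for completing your first survey for the study" and then invites login. Appendix S, the text-message counterpart, gives the invitation and link without reference to any survey.

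**Pre-test survey.** Section 4.3 places it two to three days after the baseline, with Arm 3 viewing the tool first. On the paper route it is mailed one week after the baseline is mailed, whether or not the baseline has come back.

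**The concern.** A baseline knowledge score is useful for measuring change only if it is taken before the patient meets the educational content. Section 4.3 starts the Arm 3 login from enrolment, while the baseline may still be in the post or in an inbox. An Arm 3 patient who logs in first and answers the baseline afterwards has part of the tool's effect built into the starting score.

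What is at stake is the exploratory general-knowledge analysis in section 6.2.3, which compares pre-to-post differences between Arm 3 and Arms 1/2. Arms 1 and 2 have no tool access at that stage, so the distortion can arise only in Arm 3. If the tool improves knowledge, a late baseline understates the Arm 3 gain and moves the comparison towards no difference.

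**Working it through.** **1. The order of steps, side by side.**

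| Source | What starts Arm 3 tool access | Baseline required first? |
|---|---|---|
| Section 4.3, opening paragraph | Enrolment | Not stated |
| Section 4.3, pre-test survey paragraph | Viewing before the pre-test survey, which follows the baseline by 2–3 days | Implied |
| Appendix G | Completion of the first survey | Yes, by its wording |
| Appendix S | Not stated | Not mentioned |
| Section 4.3, paper route | Pre-test survey runs from mailing of the baseline | No; return is not checked |

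The intended order is baseline, tool, pre-test survey. No sentence enforces it, and the opening paragraph of section 4.3 allows another order.

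**2. The clocks.** Suppose the login and the baseline survey both go out at enrolment, as the opening paragraph of section 4.3 permits. The prompt to view the tool comes at 24 hours and the first baseline reminder at 96 hours. The push towards the tool then comes 96 − 24 = 72 hours before the first push towards an outstanding baseline.

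**3. Which score precedes exposure.** Table 1 collects genomic knowledge at baseline, the pre-education survey, T1 and T2. Arm 3 views the tool before the pre-education survey by design, and T1 and T2 follow disclosure. That leaves the baseline alone. Section 6.2.3 does not name its *pre* and *post* surveys; the baseline is the only candidate for an unexposed *pre* score in Arm 3.

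**4. What does not depend on it.** The primary outcome (section 6.2.1) is a chi-square test of 10-day recall, with no baseline score in it. The covariates named for the accompanying logistic model are age and education, which viewing the tool cannot change.

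**5. The plan's own power figure.** Section 6.2.1 states 80% power for 39% versus 54% recall, with n = 130 and 260 and two-sided alpha 0.05.

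- Pooled proportion: (0.39 + 2 × 0.54)/3 = 0.49.
- Null SE: √[0.49 × 0.51 × (1/130 + 1/260)] = 0.0537.
- Alternative SE: √[0.39 × 0.61/130 + 0.54 × 0.46/260] = 0.0528.
- Power: Φ[(0.15 − 1.960 × 0.0537)/0.0528] = 80.2%.

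The figure reproduces, but it belongs to recall in Arm 1 versus Arms 2/3. The plan gives no power for the knowledge comparison.

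**6. Illustration only.** Assumptions, none from the plan: 130 in Arm 3 versus 260 in Arms 1/2; a true effect equal to the difference detectable with 80% power; no measured gain in Arm 3 patients whose baseline follows exposure; unchanged SD; affected share f.

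- Detectable difference: d = (1.960 + 0.842) × √(1/130 + 1/260) = 0.30 SD.
- Expected difference: (1 − f) × d.
- Power: Φ[(1 − f) × 2.802 − 1.960].

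| f | Expected difference (SD) | Power |
|---|---|---|
| 0 | 0.30 | 80% (by construction) |
| 10% | 0.27 | 71% |
| 25% | 0.23 | 56% |
| 50% | 0.15 | 29% |

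The table shows direction and shape. It does not estimate what will happen in this trial.

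**The case against.** The strongest reply is that the documents already put the baseline first. Section 4.1.1 ties it to consent, Appendix I calls it the first step, section 4.3 lists reminders in the order baseline, tool viewing, pre-test survey, and the Appendix G and J letters thank the patient for a survey already done. The word immediate in section 4.3 can be read as a contrast with Arm 2, which waits for results. Texts are said to supplement electronic reminders, so Appendix S need not replace Appendix G. This stands as evidence of intent. It does not supply a rule that holds the login back, and it does not cover the paper route, where the pre-test survey goes out whether or not the baseline has returned.

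A reader might infer more than the documents support:

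- **Selection by known allocation.** Randomisation before the baseline suggests that baseline return could depend on arm. No available text says patients learn their arm before the baseline, and the baseline invitation is the same for all arms. Consent pages and some appendices were not available, so the time of disclosure cannot be judged. Nothing says non-returners are excluded from analysis.
- **A loss from planned power.** The powers in the illustration start from an assumed 80%. They also need an assumed affected share and zero measured gain in those patients.
- **A need to randomise only on receipt of the baseline.** This is a debatable trade-off. Section 4.4 expects results about 3–14 days after sampling (section 4.3 says about 2–6 weeks), and waiting for mailed surveys before randomising could use up Arm 3's pre-results window.

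**Conclusion.** The point holds as a gap in the order of steps. Section 4.3 and Appendix G conflict on when Arm 3 may log in, Appendix S is silent, and the paper route does not wait for a returned baseline. As written, some Arm 3 patients could give their only pre-exposure knowledge score after exposure.

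The consequence is bias towards no difference in one exploratory comparison, provided that the tool raises knowledge and that the baseline serves as the *pre* score. Its size is unknown, because it depends on how many Arm 3 patients log in before answering the baseline, which the documents do not give. The primary 10-day recall test is not affected. This is a minor point, worth acting on because the remedy is nearly free.

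**What to change.** 1. State in section 4.3 that Arm 3 login is released only once the completed baseline survey is logged. Reword the immediate-access sentence and Appendix S to match Appendix G.
2. On the paper route, time both tool access and the pre-test survey from return of the baseline.
3. Where feasible, do not tell the patient the arm until the baseline is received. Randomisation itself need not move.
4. Record the dates of randomisation, baseline completion and first login for each patient.
5. In section 6.2.3, name the baseline as the *pre* score and say which survey is *post*. Add a sensitivity analysis excluding baselines dated after first login. Those exclusions can fall only in Arm 3 and depend on behaviour after randomisation, so this analysis should accompany the all-patient result and not replace it.

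**Cost.** Some protocol and script wording and three date fields. The downside is slightly later tool access for Arm 3 patients who return the baseline late. If a baseline is still outstanding when results arrive, the pre-results viewing could be missed; the plan should say how such patients are handled and keep them in Arm 3 for analysis.
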